6.7 ACUTE IPF EXACERBATION

Acute IPF exacerbation refers to a rapid deterioration of respiratory symptoms, worsening dyspnea, and decline in lung function without any identifiable cause, leading to respiratory failure or even death.

The diagnostic criteria for acute IPF exacerbation are as follows:

- History of IPF, or current clinical, imaging, and/or histological findings consistent with the diagnosis of IPF. If the previous diagnosis was not IPF based on the diagnostic criteria, current imaging and/or lung tissue pathology should indicate usual interstitial pneumonia pattern.
- Exacerbation of dyspnea or worsening of lung function within the past 30 days, not explainable by other causes.
- High-resolution computed tomography (HRCT) of the chest showing bilateral reticular or honeycomb patterns consistent with usual interstitial pneumonia, along with new ground-glass opacities and/or consolidations. If there is no prior contrast-enhanced HRCT, "new pulmonary imaging findings" can be disregarded.
- Absence of evidence for lung infection in tracheal secretions or bronchoalveolar lavage, including routine bacterial, opportunistic pathogen, and common viral examinations.
- Exclusion of other causes, including left heart failure, pulmonary embolism, and acute lung injury caused by other reasons. Causes of acute lung injury may include sepsis, aspiration, trauma, reperfusion pulmonary edema, pulmonary contusion, fat embolism, inhalation injury,

cardiac bypass surgery, drug toxicity, acute pancreatitis, transfusion of blood products, and cell transplantation.

When clinical data is incomplete or does not meet all five diagnostic criteria mentioned above, it is defined as suspected acute IPF exacerbation. Histopathologically, it is typically characterized by the coexistence of usual interstitial pneumonia (UIP) and diffuse alveolar damage (DAD), which may present with organizing pneumonia and significant fibroblast foci. Acute exacerbation leads to a worsening of lung function in IPF subjects, shortened survival time, poor treatment response, and high mortality rate.

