15.2.5 ACUTE EXACERBATION OF DISEASE

Acute IPF exacerbation refers to a sudden deterioration of the condition, worsened breathlessness, and decreased lung function without any clear cause, leading to respiratory failure or even death.

The diagnostic criteria for acute IPF exacerbation are as follows:

(1) History of IPF, or current clinical, imaging, and/or histological findings consistent with the diagnosis of IPF. If the previous diagnosis was not IPF based on the diagnostic criteria, current imaging and/or lung tissue pathology should indicate usual interstitial pneumonia pattern.

(2) Exacerbation of dyspnea or worsening of lung function within the past 30 days, not explainable by other causes.

(3) High-resolution computed tomography (HRCT) of the chest showing bilateral reticular or honeycomb patterns consistent with usual interstitial pneumonia, along with new ground-glass opacities and/or consolidations. If there is no prior contrast-enhanced HRCT, "new pulmonary imaging findings" can be disregarded.

(4) Absence of evidence for lung infection in tracheal secretions or bronchoalveolar lavage, including routine bacterial, opportunistic pathogen, and common viral examinations.

(5) Exclusion of other causes, including left heart failure, pulmonary embolism, and acute lung injury caused by other reasons. Causes of acute lung injury may include sepsis, aspiration, trauma, reperfusion pulmonary edema, pulmonary contusion, fat embolism, inhalation injury, cardiac bypass surgery, drug toxicity, acute

pancreatitis, transfusion of blood products, and cell transplantation.

When clinical data is incomplete or does not meet all five diagnostic criteria mentioned above, it is defined as suspected acute IPF exacerbation. Histopathologically, it is typically characterized by the coexistence of usual interstitial pneumonia (UIP) and diffuse alveolar damage (DAD), which may present with organizing pneumonia and significant fibroblast foci. Acute exacerbation leads to a worsening of lung function in IPF subjects, shortened survival time, poor treatment response, and high mortality rate.

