17.3.2 SAFETY EVALUATION

Adverse events (AEs) will be recorded after the first bronchoscopy collection and following the second bronchoscopy treatment. The description of AEs after the first bronchoscopy collection and the analysis of AEs after the second bronchoscopy treatment are as follows:

(1) Calculation of the incidence and severity of cell therapy-related adverse events (AEs) for each group.

(2) Calculation of the incidence of bronchoscopy-related complications for each group.

(3) Calculation of the mean, standard deviation, median, and interquartile range for the dynamic changes of each lung tumor biomarker in all groups.

(4) Presentation of the cross-tabulation of routine safety check abnormalities (complete blood count, urinalysis, blood biochemistry, electrolytes, electrocardiogram) between baseline and each visit.

(5) Recording the frequency and severity of acute IPF exacerbations

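### The rule for suspected acute IPF exacerbation gives a deterioration with a proven other cause the same label as one that could not be fully assessed

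*Protocol*

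**What the plan says.** Protocol section 6.7 opens with a general definition of acute IPF exacerbation that includes "decline in lung function without any identifiable cause, leading to respiratory failure or even death". Five diagnostic criteria follow. Three of them remove other explanations:

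- Criterion 2: "Exacerbation of dyspnea or worsening of lung function within the past 30 days, not explainable by other causes".
- Criterion 4: "Absence of evidence for lung infection in tracheal secretions or bronchoalveolar lavage, including routine bacterial, opportunistic pathogen, and common viral examinations".
- Criterion 5: "Exclusion of other causes, including left heart failure, pulmonary embolism, and acute lung injury caused by other reasons". The causes of lung injury listed under it end with "transfusion of blood products, and cell transplantation".

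The section then sets the rule for the second category: "When clinical data is incomplete or does not meet all five diagnostic criteria mentioned above, it is defined as suspected acute IPF exacerbation". Section 15.2.5 has the same five criteria and the same rule ("does not meet all five diagnostic criteria mentioned above, it is defined as suspected acute IPF exacerbation"). Neither section provides a category for a deterioration that was fully worked up and found to have another cause.

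Frequency and severity of exacerbations within 24 weeks of treatment is a secondary endpoint (sections 6 and 8.2). The analysis text in section 17.3.2, item 5, reads "Recording the frequency and severity of acute IPF exacerbations". None of these places mentions suspected events. Section 1.6(2) makes an acute exacerbation related to the cell therapy a ground for ending dose escalation, also without mentioning suspected events.

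**The concern.** The rule joins two different situations with a single 'or'. In one, a criterion could not be assessed, for example because no airway sample was taken; calling that event suspected is reasonable. In the other, a criterion was assessed and failed. When the failed criterion is 4 or 5, the work-up has found an infection, heart failure or an embolism, which is evidence against an acute exacerbation. Criteria 4 and 5 exist to remove such events, and the rule for the suspected category brings them back under a weaker label.

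At stake is what the exacerbation endpoint means in a trial of 15 to 24 patients with groups of 3 to 6, where one event changes a group's rate visibly. Infection is also a listed bronchoscopy complication (sections 6.6 and 15.1), and such complications are a separate secondary endpoint. One post-procedural pneumonia could therefore be reported both as a procedural harm and as a suspected disease event.

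**Working it through.** The protocol gives no figure for this point, so there is none to reproduce. The check applies the rule as written.

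**Worked cases**

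| Record | Criterion affected | Label under the rule | Consistent with the opening definition? |
|---|---|---|---|
| Worsening dyspnoea, new opacities, no airway sample | 4 not assessed | Suspected | Yes: no cause identified |
| Same picture, positive bacterial culture | 4 failed | Suspected | No: cause identified |
| Worsening dyspnoea, documented left heart failure or pulmonary embolism | 5 failed | Suspected | No: cause identified |

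**Enumeration**

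Set each criterion to met or failed, with complete data: 2^5 = 32 patterns.

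- All five met: 1 pattern, a definite exacerbation.
- All others: 32 − 1 = 31 patterns, all suspected.
- Of these 31, criterion 4 or 5 is failed in 32 − 2^3 = 24.

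Now allow met, failed or missing: 3^5 = 243 patterns.

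- Suspected: 243 − 1 = 242.
- Criterion 4 or 5 failed: 243 − 3^3 × 2^2 = 243 − 108 = 135.
- Suspected through missing data alone: 2^5 − 1 = 31.

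These are counts of logical patterns, not patient frequencies. They show that with complete data the rule leaves no route to the conclusion that an event was not an exacerbation.

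**Size of one false event, if suspected events are counted**

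Section 1.3 plans 3 to 6 patients in each of the first three groups and 6 in the fourth.

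- Group of 3: 1/3 = 33 percentage points.
- Group of 6: 1/6 = 17 percentage points.

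**Illustration only, with assumed rates and suspected events counted**

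The protocol gives no rate for deteriorations with a proven other cause. Assume a proportion p of patients has one within 24 weeks. The chance of at least one false event is 1 − (1 − p)^n.

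| p (assumed) | n = 15 | n = 24 |
|---|---|---|
| 3% | 37% | 52% |
| 5% | 54% | 71% |
| 10% | 79% | 92% |

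If a fraction q of all events so counted has a proven other cause, the count is inflated by 1/(1 − q): 1/0.7 = 1.4 at q = 30% and 1/0.5 = 2.0 at q = 50%, both assumed.

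**The case against.** **The opening definition already excludes events with a cause.** It does, and flowchart note 16 and section 15.2.5 say much the same. But the rule for the suspected category is the more specific text, does not carry that condition, and makes failing a criterion a way into the category. At best the section contradicts itself about a case with a proven cause.

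**The protocol never says that suspected events are counted.** This stands. A reader might infer that proven pneumonias will inflate the reported frequency. The endpoint sections do not support that: they name exacerbations and are silent on suspected ones. A count of definite events only would still measure acute exacerbation, specifically if less sensitively, and losing events without an airway sample is a feature of any such count. What remains is that the suspected category, which should hold those uncertain true events, also holds events shown to be something else.

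**The label does not drive dose escalation.** A reader might infer that it does, through section 1.6(2). That criterion requires at least a possible relation to the product, and section 11.4 classes an event with a clear alternative cause as definitely unrelated. A documented embolism or heart failure would normally stay outside 1.6(2) whatever its label, and a severe infection judged related would enter as a severe adverse event anyway.

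**Other tempting extensions do not hold.** Two bronchoscopies per patient might seem to double the exposure to procedural infection, but only the second falls in the 24-week post-treatment window. Failure of the imaging criterion is not a secure example, because criterion 3 waives the requirement for new findings when there is no earlier contrast-enhanced scan, and the visit schedule does not mention contrast.

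**Tabulation belongs in the SAP.** The table layout may. The event definition is fixed in the protocol, in two places, and it is the definition that misclassifies.

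**Conclusion.** The point holds as a fault in a stated definition. As written in sections 6.7 and 15.2.5, a deterioration with proven lung infection, left heart failure or pulmonary embolism is a suspected acute IPF exacerbation, against the opening definition of section 6.7. This follows from the text and rests on no assumption.

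The effect on the endpoint is conditional. If suspected events are counted, each such event is a false exacerbation worth 17 to 33 percentage points in a group of 3 to 6. If they are not counted, the definite count stands, but true events without an airway sample cannot be told from false ones by their label. The 37% to 92% and 1.4 to 2.0 figures depend on assumed rates and on suspected events being counted, and are not estimates for this trial. No effect on the escalation decision is shown.

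One neighbouring conflict limits how the rule can be changed. Criterion 5 lists cell transplantation among the causes to exclude, so an event attributed to the product cannot meet all five criteria, while section 1.6(2) relies on related acute exacerbations.

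**What to change.** 1. In sections 6.7 and 15.2.5, limit the suspected category to deteriorations without an identified other cause in which one or more criteria could not be assessed.
2. Record events with documented infection, left heart failure or pulmonary embolism under their own diagnosis as adverse events.
3. State whether the endpoint in sections 6, 8.2 and 17.3.2 counts definite events only, or definite plus suspected events with the two reported separately.
4. Reconcile criterion 5 with section 1.6(2) on events attributed to the cell product, and say explicitly how they are classified. Without this, the narrower wording in item 1 would leave them neither definite nor suspected.

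The cost is one sentence in each of two sections, a clarification of the endpoint, and the reconciliation in item 4. No new test is added. The downside is that slightly fewer events carry the exacerbation label; they remain recorded as adverse events under section 11.2.

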7 EFFICACY ASSESSMENTS

- Changes in lung diffusing capacity for single-breath carbon monoxide (DLCO-sb) compared to baseline at 4-, 12-, and 24-weeks post-treatment.
- Changes in Forced Vital Capacity (FVC) compared to baseline at 4-, 12-, and 24-weeks post-treatment.
- Changes in the ratio of diffusing capacity for carbon monoxide/ the alveolar volume (DLCO/VA) compared to baseline at 4-, 12-, and 24-weeks post-treatment.
- Changes in 6-minute-walk test (6MWT) compared to baseline at 4-, 12-, and 24-weeks post-treatment.

Specific procedures are as follows: In the respiratory outpatient department, select a well-lit, well-ventilated, temperature-controlled corridor with a hard, straight, and flat surface, with a distance of 30 meters for the round trip, and place prominent markers at the starting and ending points. Before the test, explain the purpose, methods, and relevant precautions to the subjects. Participants should wear comfortable clothing and shoes during the test and may use walking aids such as canes. Subjects can have a light meal before the test, but should avoid excessive physical activity and warm-up exercises within 2 hours prior to the test. Subjects should sit quietly for at least 10 minutes at the starting point before the test. During the test, the timer should be started, and the subjects should walk at their own pace based on their usual daily activities from the starting point, turn around at the 30-meter endpoint, and the number of cycles completed in each round trip should be recorded. The testing personnel should not walk with the subjects or use overtly suggestive verbal or non-verbal encouragement. If subjects experience fatigue, dizziness, chest pain, intolerable dyspnea, lower limb spasms, cold sweats, or pallor during the test, the test should be immediately stopped. At the end of the test, shout "Stop" and ask the subjects to stop moving, marking their position. Blood pressure and heart rate should be measured before and after the test.

- Changes in the St. George's Respiratory Questionnaire (SGRQ) scale compared to baseline at 4-, 12-, and 24-weeks post-treatment.
- Changes in imaging of lung by high-resolution computed tomography (HR-CT) compared to baseline at 24 weeks post-treatment.

The HRCT scoring will be evaluated by the leading investigator of the coordinating center. The scoring will primarily rely on visual subjective assessment of the overall extent of ground-glass opacities, reticular abnormalities, honeycombing, and traction bronchiectasis, based on the imaging, without considering the subjects' clinical data and lung function.

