1.4 STUDY PROCEDURE

This study includes screening stage V1, cell collection stage V2, baseline stage V3 (0-5 days before cell transplantation), REGEND001 autologous therapy product transplantation stage V4, follow-up stage V5-V9, safety follow-up stage after research. Follow-up stage includes: V5 (24 hours \pm 4 hours after transplantation), V6 (1 week \pm 2 days after transplantation), V7 (4 weeks \pm 3 days after transplantation), V8 (12 weeks \pm 5 days after transplantation), V9 (24 weeks \pm 7 days after transplantation). During the study, the vital signs, laboratory examinations, 12-lead electrocardiogram, chest HRCT, pulmonary functions, 6-minute walking distance, questionnaires, concomitant medications, adverse events, etc. will be checked and recorded.

Screening stage V1: After the patient signing the informed consent, relevant physical examination and check of previous physical examination will be done. The investigator will check inclusion and exclusion criteria, making judgement on whether the patient is eligible.

Cell collection stage V2: Tissue collection through bronchoscopy, cell isolation and expansion of around 4-8 weeks before autologous transplantation of REGEND001 autologous therapy product.

Baseline stage V3 (0-5 days before cell transplantation): 4-8 weeks later, conduct relevant examinations again and check inclusion and exclusion criteria. For idiopathic pulmonary fibrosis patients who are still eligible, they can formally join in this clinical trial and will receive autologous transplantation of REGEND001 cell products.

Cell transplantation stage V4 (the day of cell transplantation): According to the dose group each patient was assigned, a single administration of REGEND001 cell products at the corresponding dose were autologously transplanted to different lung segments through bronchoscopy. Investigator should be on site during the transplantation, confirming the dose, starting and stopping time of the transplantation, and recording correctly. Close observation of the patients in the outpatient or hospital for 2-4 hours after administration, and the investigator will determine when the patients can leave based on the tolerance of the patients. After leaving the hospital, the patients should return back to the research center as required for follow-up.

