8.2 SECONDARY OUTCOME MEASURES

- Incidence of complication related to bronchoscopy within 24 weeks after treatment.

- Changes in lung diffusing capacity for single-breath carbon monoxide (DLCO-sb) compared to baseline at 4-, 12-, and 24-weeks post-treatment.
- Changes in Forced Vital Capacity (FVC) compared to baseline at 4-, 12-, and 24-weeks post-treatment.
- Changes in the ratio of diffusing capacity for carbon monoxide/ the alveolar volume (DLCO/VA) compared to baseline at 4-, 12-, and 24-weeks post-treatment.
- Changes in 6-minute-walk test (6MWT) compared to baseline at 4-, 12-, and 24-weeks post-treatment.
- Changes in the St. George's Respiratory Questionnaire (SGRQ) scale compared to baseline at 4-, 12-, and 24-weeks post-treatment.
- Changes in imaging of lung by high-resolution computed tomography (HR-CT) compared to baseline at 24 weeks post-treatment.
- Frequency and severity of IPF exacerbation events within 24 weeks after treatment.
- Number of cases of participants with abnormal Blood routine results within 24 weeks post-treatment.
- Number of cases of participants with abnormal Urine routine results within 24 weeks post-treatment.

- Number of cases of participants with abnormal Blood biochemistry results within 24 weeks post-treatment.
- Number of cases of participants with abnormal 12-lead Electrocardiogram (ECG) results within 24 weeks post-treatment.
- Changes in tumor markers (Cytokeratin 19 fragment (CYFRA21-1), Neuron-specific enolase (NSE), Squamous cell carcinoma antigen (SCC), Carcinoembryonic antigen (CEA)) compared to baseline at 4-, 12-, and 24-weeks post-treatment.

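### The 6-minute walk procedure sets an everyday pace with no distance aim and stops for unqualified fatigue, so the recorded value is habitual speed times time walked, and walks cut short enter the same change score

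*Protocol*

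**What the plan says.** Protocol section 8.2 lists as a secondary outcome "Changes in 6-minute-walk test (6MWT) compared to baseline at 4-, 12-, and 24-weeks post-treatment", and section 7 lists the same item among the efficacy assessments. Section 1.4 names the quantity recorded as "6-minute walking distance, questionnaires, concomitant medications, adverse events, etc"; sections 1.5 and 10 also name it as a walking distance.

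The procedure is in section 7. On pace, "the subjects should walk at their own pace based on their usual daily activities". On stopping, "If subjects experience fatigue, dizziness, chest pain, intolerable dyspnea, lower limb spasms, cold sweats, or pallor during the test, the test should be immediately stopped". On staff conduct, "The testing personnel should not walk with the subjects or use overtly suggestive verbal or non-verbal encouragement". When the test ends, staff "ask the subjects to stop moving, marking their position". The records asked for are the cycles completed, the final position, and blood pressure and heart rate before and after.

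The procedure does not ask patients to go as far as they can and does not restate the six-minute duration. It does not ask for the minutes walked when a test ends early, or say how such a test counts. No other section supplies these points.

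**The concern.** The outcome carries the name of a distance over a fixed time, but the procedure fixes neither the effort nor, for every patient, the time. Pace is anchored to everyday activity. Choosing one's own pace is not itself the fault; the gap is that no distance goal goes with it, so a patient may complete the test correctly without showing how far he or she could have gone.

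The stop rule adds a second problem. Fatigue carries no severity qualifier, whereas dyspnea in the same sentence must be intolerable. A walk ended by fatigue at minute 4 gives a four-minute distance, and the change score would treat it as a six-minute one.

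The trial has no control group (section 4) and 3 to 6 patients per dose group (section 1.3), so one truncated walk can carry real weight in a group mean. Section 1 gives efficacy by dose, and a dose recommendation for later studies, as the secondary purpose. The fault also lies in how the measurement is taken: no later analysis can recover minutes walked if they were not written down, or a best-effort distance from an everyday-pace walk.

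**Working it through.** The protocol states no expected change, SD or power for the walk test, so there is no figure to reproduce. The check reads the text and then illustrates the size.

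**What the procedure measures.** For one patient at one visit,

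D = v × min(360 s, t),

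where v is the everyday pace and t is the time at which a listed symptom, including fatigue, ends the test. If no symptom occurs, D = 360v, a true six-minute distance at habitual pace. If a symptom occurs at t < 360 s, D = v × t, and the shortfall against a full walk at the same pace is v × (360 − t).

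**What enters the outcome.** The change is D(follow-up) − D(baseline). With v unchanged, a stop at follow-up only makes the change negative by v × (360 − t). A stop at baseline only makes it positive by the same amount. Stops at the same time at both visits cancel. The distortion therefore needs an early stop at one visit and not the other, or stops at different times.

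**Size, with assumed inputs.** The paces (0.9, 1.1 and 1.3 m/s) and the stop at minute 4 (240 s) are assumptions; only the group sizes of 3 and 6 come from section 1.3. The mean shift is the loss divided by the group size, for one affected patient.

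| Pace | 360 s | 240 s | Loss | Mean shift, group of 3 | Mean shift, group of 6 |
|---|---|---|---|---|---|
| 0.9 m/s | 324 m | 216 m | 108 m | 36 m | 18 m |
| 1.1 m/s | 396 m | 264 m | 132 m | 44 m | 22 m |
| 1.3 m/s | 468 m | 312 m | 156 m | 52 m | 26 m |

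**Sensitivity to the stop time.** A stop at minute 5 loses 60 s: 0.9 × 60 = 54 m to 1.3 × 60 = 78 m. The mean shift is then 54/3 = 18 m to 78/3 = 26 m in a group of 3, and 54/6 = 9 m to 78/6 = 13 m in a group of 6. The result scales directly with the time lost.

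**The case against.** The strongest reply is that the protocol never promises a maximal test. Distance covered in six minutes at a usual pace is still a six-minute walking distance, and the same procedure applies at every visit, so change within a patient keeps a meaning. That stands: for patients who complete the test, the outcome can be read as change in habitual walking. It does not cover patients who are stopped early.

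A second reply is that an everyday pace makes fatigue within six minutes less likely, and that the protocol gives no frequency of early stops. This also stands. Entry allows DLCO down to 30% of predicted (section 2.2), so early stops are foreseeable, but how common they would be is unknown.

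A third reply is that the summaries include medians and interquartile ranges (section 17.3.3), which a single value moves less than it moves a mean. That is true, although with 3 patients the protection is limited.

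Some stronger readings are tempting, but the documents do not support them:

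- A reader might infer that the test measures time to tiredness. That applies only to patients who stop early.
- A reader might infer that trivial tiredness must end the test. The word is unqualified, and the contrast with intolerable dyspnea makes that reading possible, but the text does not state it.
- A reader might infer that one early stop outweighs any plausible treatment effect. The protocol gives no effect size or SD, so that comparison cannot be made.
- A reader might infer that a distance aim would remove expectation effects in this open-label trial. Effort stays voluntary under either instruction, and section 7 already bars overt encouragement by staff.
- A reader might infer that the fatigue stop is wrong and that rests should be allowed instead. That is a clinical rule. The text shows only that the stop and the endpoint do not fit together as written.

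**Conclusion.** The point holds at moderate weight. As written, section 7 yields habitual pace times time walked, and it lets truncated walks enter the change score as if they were six-minute distances. One stop at minute 4 at a single visit would shift a group's mean change by 36 to 52 m with 3 patients or 18 to 26 m with 6. This rests on assumed paces of 0.9 to 1.3 m/s, the assumed stop time and an unchanged pace between visits; a stop at minute 5 halves the figures. Whether such shifts are large against real change or patient-to-patient spread cannot be judged from the protocol.

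The weight is limited because the walk test is one of several secondary outcomes, is summarised descriptively, and does not drive dose escalation, which section 1.6 bases on safety. It is still worth correcting, because the measure bears on the efficacy assessment behind the dose recommendation and the missing information cannot be recovered later.

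**What to change.** - In section 7, state that the aim is to cover as much distance as possible in six minutes, and give one scripted instruction for use at all sites and visits.
- Have the sponsor and investigators reconcile the fatigue stop with the six-minute distance endpoint, including what fatigue means there. No stopping or pausing rule is proposed here.
- For every test ended early, record the minutes walked and the reason, and flag these tests in the summaries.

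Separately, while section 7 is open, the course length needs reconciling: it is described "with a distance of 30 meters for the round trip", yet patients "turn around at the 30-meter endpoint", so a counted cycle could be 30 m or 60 m.

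The cost is a few sentences in section 7, a short script and two case report form fields. The drawback is that walks done before the change are not comparable with later ones and must be summarised separately, which thins already small groups if enrolment has begun.
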